## 5.4.2. Clinical Laboratory Assessments

Descriptive summaries of selected (quantitative) clinical laboratory results and change from Baseline will be presented by treatment group and visit. Laboratory results will be presented using the International System of Units (SI). Laboratory abnormalities will be determined using predefined normal ranges. Clinical laboratory values will be considered potentially clinically significant (PCS) for select parameters per Table 4. The number and percentage of patients

experiencing PCS laboratory abnormalities post-baseline will be summarized by treatment group. Additionally, shifts in Laboratory values with reference to the normal range from Study Baseline to Week 12 or early termination will be summarized by treatment group.

Listings will be provided for patients with any laboratory results outside the reference ranges, as well as for patients with any PCS (select parameters) laboratory results.

Table 4 Criteria for Potentially Clinically Significant Laboratory Tests

Laboratory Parameter	SI Units	Conversion Factor a	Traditional Units	PCS Criteria b Low Values	PCS Criteria b High Values		
Hematology							
Hemoglobin F	g/L	0.1	g/dL	< 100	_		
M				< 120			
Hematocrit F	ratio	100	%	≤ 32% and	_		
				≥3% decrease			
				from baseline			
M				≤ 37% and			
				≥3% decrease			
				from baseline			
White cell count	$10^{9}/L$	1	$10^3/\mu L$	≤ 2.5	≥ 15		
Eosinophils	$10^{9}/L$	1	$10^3/\mu L$	_	≥ 1.50		
absolute cell count							
Neutrophils	$10^{9}/L$	1	$10^3/\mu L$	≤ 1.50	≥ 12.0		
absolute cell count	4.00 %		4.037. 7	100	> 4.0		
Lymphocyte	10  /L	1	$10^3/\mu L$	≤ 0.8	≥ 4.0		
absolute cell count Platelet count	10  /L	1	$10^3/\mu$ L	≤ 75	≥ 700		
Flatelet count	10 /L	_	emistry	≥ 73	≥ /00		
Albumin	g/L	0.1	g/dL	< 28			
Alkaline phosphatase	U/L	1	U/L		$\geq$ 2 × UNL		
ALT	U/L	1	U/L	_	$\geq 3 \times \text{UNL}$		
AST	U/L	1	U/L	_	$\geq 3 \times \text{UNL}$		
Blood urea nitrogen	mmol/L	2.8011	mg/dL	_	> 1.4 × UNL		
Calcium	mmol/L	4.008	mg/dL	< 1.97	> 2.77		
Cholesterol	mmol/L	38.6698	mg/dL	_	> 7.75		
Creatinine	μmol/L	0.0113	mg/dL	_	> 1.4 × UNL		
Glucose, fasting	mmol/L	18.015	mg/dL	< 3.0	> 7.6 × UNL		
Potassium	mmol/L	1	mEq/L	< 3.3	> 5.5		
Sodium	mmol/L	1	mEq/L	< 130	> 150		
Total bilirubin	μmol/L	0.0585	mg/dL	_	> 1.5 × UNL		
Urinalysis							
Protein			_	_	≥ 2 +		
Glucose	_		_	_	≥1+		

ALT = alanine aminotransferase; AST = asparate aminotransferase; LNL = lower normal limit of laboratory reference range; PCS = potentially clinically significant; SI = Le Système International d'Unités (International System of Units); UNL = upper normal limit of laboratory reference range.

- a Conversion factor is the multiplication factor to convert from SI units to traditional units.
- b Criteria refer to SI units.

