# 10.8.2. Clinical Laboratory Tests

Laboratory data will be summarized by type of laboratory test. Reference ranges and markedly abnormal results (specified in the SAP) will be used in the summary of laboratory data. Descriptive statistics will be calculated for each laboratory analyte at Baseline and at each scheduled time point. Changes from Baseline results will be presented in pre- versus post-treatment cross tabulations (with classes for below, within, and above normal ranges). A listing of patients with any laboratory results outside the reference ranges will be provided. A listing of patients with any markedly abnormal laboratory results will also be provided.

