Table	14.3.1.2.1	Treatment-Emergent Adverse Events by System Organ Classification, Preferred Term and Maximum Severity	Safety
Table	14.3.1.2.2	Treatment-Emergent Adverse Events by System Organ Classification, Preferred Term and Maximum Severity, 01 February 2020 Cutoff	Safety
Table	14.3.1.3.1	Treatment-Emergent Adverse Events Related to Study Treatment by System Organ Classification, Preferred Term and Maximum Severity	Safety
Table	14.3.1.3.2	Treatment-Emergent Adverse Events Related to Study Treatment by System Organ Classification, Preferred Term and Maximum Severity, 01 February 2020 Cutoff	Safety
Table	14.3.1.4.1	Treatment-Emergent Adverse Events Leading to Discontinuation of Study Treatment by System Organ Classification, Preferred Term and Maximum Severity	Safety
Table	14.3.1.4.2	Treatment-Emergent Adverse Events Leading to Discontinuation of Study Treatment by System Organ Classification, Preferred Term and Maximum Severity, 01 February 2020 Cutoff	Safety
Table	14.3.1.5.1	Treatment-Emergent Fatal Adverse Events by System Organ Classification and Preferred Term	Safety
Table	14.3.1.5.2	Treatment-Emergent Fatal Adverse Events by System Organ Classification and Preferred Term, 01 February 2020 Cutoff	Safety
Table	14.3.1.6.1	Treatment-Emergent Serious Adverse Events by System Organ Classification and Preferred Term	Safety
Table	14.3.1.6.2	Treatment-Emergent Serious Adverse Events by System Organ Classification and Preferred Term, 01 February 2020 Cutoff	Safety
Table	14.3.1.7.1	Treatment-Emergent Adverse Events of Special Interest: Palpitations or Abnormal Heart Rhythms, Dizziness or Syncope, and Seizure	Safety

171111 101007	
Statistical Analysis	Plan

Item	Number	Description	Population
Table	14.3.1.7.2	Treatment-Emergent Adverse Events of Special Interest: Palpitations or Abnormal Heart Rhythms, Dizziness or Syncope, and Seizure, 01 February 2020 Cutoff	Safety
Table	14.3.4.1	Clinical Laboratory Hematology Parameters by Time Point	Safety
Table	14.3.4.2	Clinical Laboratory Chemistry Parameters by Time Point	Safety
Table	14.3.4.3	Clinical Laboratory Urinalysis Parameters (Continuous) by Time Point	Safety
Table	14.3.4.4	Clinical Laboratory Parameter Shifts from Baseline	Safety
Table	14.3.4.5	Potentially Clinically Significant Laboratory Values	Safety
Table	14.3.5.1	Vital Sign and Anthropomorphic Parameters and Changes from Baseline, by Time Point	Safety
Table	14.3.5.2.1	Potentially Clinically Significant Vital Signs Occurring Post-Baseline	Safety

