Listing	16.2.5.1	Study Drug Administration and Compliance	Safety
Listing	16.2.5.2	Prior and Concomitant Medications	Enrolled
Listing	16.2.5.3	Plasma Concentrations of MIN-101 and BFB-520	ITT (with PK)
Listing	16.2.6.1		ITT
Listing	16.2.6.2	Personal and Social Performance (PSP) Assessments	ITT
Listing	16.2.6.3	Clinical Global Impression of Severity (CGI-S) Assessments	ITT
Listing	16.2.6.4		
			ITT

	Number	Description	Population
Listing	16.2.7.1	Adverse Events	Enrolled
Listing	16.2.7.2	Treatment-Emergent Adverse Events	Enrolled
Listing	16.2.7.3	Adverse Events Leading to Discontinuation of Study Treatment	Enrolled
Listing	16.2.7.4	Fatal Adverse Events	Enrolled
Listing	16.2.7.5	Serious Adverse Events	Enrolled
Listing	16.2.7.6	Serious Adverse Events Occurring Prior to Randomization	Enrolled
Listing	16.2.7.7	Adverse Events for Subjects with Potentially Clinically Significant QTcF Values	Enrolled
Listing	16.2.7.8	Adverse Events for Subjects with Potentially Clinically Significant HR, QRS, or PR Values	Enrolled
Listing	16.2.7.9	Adverse Events of Special Interest	Enrolled
Listing	16.2.8.1.1	Laboratory Data – Chemistry	Enrolled
Listing	16.2.8.1.2	Laboratory Data – Hematology	Enrolled
Listing	16.2.8.1.3	Laboratory Data – Urinalysis	Enrolled
Listing	16.2.8.1.4	Laboratory Data - Serology	Enrolled
Listing	16.2.8.1.5	Laboratory Data – Serum Pregnancy Testing	Enrolled
Listing	16.2.8.1.6	Laboratory Results Outside Reference Range	Enrolled
Listing	16.2.8.1.7	Potentially Clinically Significant Laboratory Results	Enrolled
Listing	16.2.8.2.1	Vital Signs and Anthropomorphic Measures	Enrolled
Listing	16.2.8.2.2	Potentially Clinically Significant Vital Signs	Enrolled
Listing	16.2.8.3	Physical Examinations	Enrolled
Listing	16.2.8.4	12-Lead ECG Findings	Enrolled
Listing	16.2.8.5	Clinically Significant 12-Lead ECG Findings	Enrolled
Listing	16.2.8.6	Potentially Clinically Significant 12-Lead ECG Findings	Enrolled
Listing	16.2.8.6	Abnormal 12-Lead ECG Findings	Enrolled
Listing	16.2.9.1	Abnormal Involuntary Movement Scale (AIMS) Assessments	Enrolled
Listing	16.2.9.2	Barnes Akathisia Rating Scale (BARS) Assessments	Enrolled
Listing	16.2.9.3	Simpson-Angus Scale (S-AS) Assessments	Enrolled
Listing	16.2.9.4	Sheehan Suicidality Tracking Scale (STS) Assessments	Enrolled

Item	Number	Description	Population
Figures	•		
Figure	14.2.1.1.2		
			PP
Figure	14.2.2.1.2	Change from Baseline in Personal and Social Performance (PSP) Score using the Least Squares Means (±SE) from MMRM, by Visit	ITT

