Listing	16.2.7.8	Adverse Events for Subjects with Potentially Clinically Significant HR, QRS, or PR Values	Enrolled	
Listing	16.2.7.9	Adverse Events of Special Interest	Enrolled	
Listing	16.2.8.1.1	Laboratory Data – Chemistry	Enrolled	
Listing	16.2.8.1.2	Laboratory Data – Hematology Enroll		
Listing	16.2.8.1.3	Laboratory Data – Urinalysis Enrolled		
Listing	16.2.8.1.5	Laboratory Data – Serum Pregnancy Testing Enrolled		

Item	Number	Description	Population
Listing	16.2.8.1.6	Laboratory Results Outside Reference Range	Enrolled
Listing	16.2.8.1.7	Clinically Significant Laboratory Results	Enrolled
Listing	16.2.8.2.1	Vital Signs and Anthropomorphic Measures	Enrolled
Listing	16.2.8.2.2	Potentially Clinically Significant Vital Signs	Enrolled
Listing	16.2.8.3	Physical Examinations	Enrolled
Listing	16.2.8.4	12-Lead ECG Findings	Enrolled
Listing	16.2.8.5	Clinically Significant 12-Lead ECG Findings	Enrolled
Listing	16.2.8.6	Potentially Clinically Significant 12-Lead ECG Findings	Enrolled
Listing	16.2.8.6	Abnormal 12-Lead ECG Findings	Enrolled
Listing	16.2.9.1	Abnormal Involuntary Movement Scale (AIMS) Assessments	Enrolled
Listing	16.2.9.2	Barnes Akathisia Rating Scale (BARS) Assessments	Enrolled
Listing	16.2.9.3	Simpson-Angus Scale (S-AS) Assessments	Enrolled
Listing	16.2.9.4	Sheehan Suicidality Tracking Scale (STS) Assessments	Enrolled
Figures	•		•
Figure	14.2.1.1.2		
			PP
Figure	14.2.2.1.2	Change from Baseline in Personal and Social Performance (PSP) Score using the Least Squares Means (±SE) from MMRM, by Visit	
Figure	14.2.2.1.4	Change from Baseline in Personal and Social Performance (PSP) Score using the Least Squares Means (±SE) from MMRM, by Visit	
Figure	14.2.11.2	Time to Relapse in Study	ITT
Figure	14.2.11.4	Time to Relapse in Study	PP
Figure	14.2.14.1.1.2		
			ITT (with PK)

Statistical Analysis Plan

Final Version 1.0

Item	Number	Description	Population
Figure	14.2.14.2.2.2		
			ITT (with PK)

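### SAP Table 4 sets the high fasting-glucose limit at 7.6 times the upper normal limit, so the high-glucose flag will register almost no one in any arm

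*SAP*

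**What the plan says.** Protocol section 10.8.2 leaves the laboratory limits to the SAP: "Reference ranges and markedly abnormal results (specified in the SAP) will be used in the summary of laboratory data". SAP section 5.4.2 supplies them: "Clinical laboratory values will be considered potentially clinically significant (PCS) for select parameters per Table 4". The number and percentage of patients with a post-baseline PCS value are then summarized by treatment group.

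In Table 4 the fasting-glucose row, in mmol/L with a conversion factor of 18.015 to mg/dL, reads < 3.0 on the low side and > 7.6 × UNL on the high side. The notes under the table give "UNL = upper normal limit of laboratory reference range" and "Criteria refer to SI units". Neither document gives a numerical UNL for glucose, and nothing elsewhere in either document corrects the cell.

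The limits feed Table 14.3.4.5, "Potentially Clinically Significant Laboratory Values", which appears in the output lists for both phases (SAP sections 9.1 and 9.2). They also feed Listing 16.2.8.1.7, titled "Potentially Clinically Significant Laboratory Results" in the double-blind list. In the open-label list the same listing number is titled "Clinically Significant Laboratory Results". That the open-label listing uses the Table 4 flag is therefore inferred from the shared number rather than stated.

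**The concern.** The cell is out of pattern with the rest of its own table in both form and size. It looks like a slip: either the UNL multiplier is stray and the number was meant as an absolute SI value, or the multiple itself is mistyped. The documents do not say which.

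Followed as written, the threshold is so high that the flag cannot distinguish a drug that raises fasting glucose from one that does not. Table 4 has no HbA1c row, so this cell is its only blood-based criterion for high glucose. Protocol section 1.1 names metabolic disorders among the limitations of existing antipsychotics, so readers will look at this row. A near-zero count in every arm could be taken as evidence of no glucose effect when it shows only that the threshold was out of reach.

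**Working it through.** The limit is a stated constant with no derivation in the plan, so there is no calculation of the sponsor's to reproduce. The check asks what the limit means in practice and how it compares with its neighbors.

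**Inputs from SAP Table 4**
- Fasting glucose: low < 3.0 mmol/L; high > 7.6 × UNL; factor 18.015 (mmol/L to mg/dL).
- Other UNL multiples: 1.4 (blood urea nitrogen, creatinine), 1.5 (total bilirubin), 2 (alkaline phosphatase), 3 (ALT, AST).
- Other chemistry rows with both a low and a high limit: calcium (< 1.97, > 2.77), potassium (< 3.3, > 5.5), sodium (< 130, > 150). All are absolute on both sides.

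**Input not in the documents**
- UNL for fasting glucose, assumed to be 5.5 to 6.1 mmol/L.

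**Step 1: a bound from the table alone.** If UNL were not above 3.0 mmol/L, the whole normal range would be flagged low. So UNL > 3.0, and
- written limit > 7.6 × 3.0 = 22.8 mmol/L
- 22.8 × 18.015 = 411 mg/dL.

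**Step 2: the limit under the assumed UNL**
- 7.6 × 5.5 = 41.8 mmol/L; × 18.015 = 753 mg/dL
- 7.6 × 6.1 = 46.4 mmol/L (46.36 before rounding); 46.36 × 18.015 = 835 mg/dL.

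**Step 3: comparison with the other multiples** (needs no UNL value)
- 7.6 / 3 = 2.5 times the largest
- 7.6 / 1.5 = 5.1 times the bilirubin multiple
- 7.6 / 1.4 = 5.4 times the urea nitrogen and creatinine multiple.

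**Step 4: the two plausible readings**
- Absolute value, multiplier stray: 7.6 mmol/L; 7.6 × 18.015 = 137 mg/dL. Relative to the assumed UNL this is 7.6 / 6.1 = 1.25 to 7.6 / 5.5 = 1.38, just under the 1.4 and 1.5 used elsewhere in the table.
- Mistyped multiple, taking the table's own range of 1.4 to 3: 1.4 × 5.5 = 7.7 to 3 × 6.1 = 18.3 mmol/L.

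For the written limit to equal 7.6 mmol/L, UNL would have to be 1.0 mmol/L, below the row's own low limit. Both readings lie below even the 22.8 mmol/L bound.

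**Step 5: illustration of the count.** The documents give no glucose distribution. Assume normal distributions with mean/SD of 5.2/0.6, 5.5/1.0 and 6.0/1.5 mmol/L, one value per patient and 167 patients per arm. Then about 0, 3 and 24 patients per arm exceed 7.6 mmol/L, and effectively none exceed 22.8 mmol/L. Real glucose values may be skewed, so these figures show only the contrast between thresholds and do not predict counts.

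**The case against.** The strongest reply is that this is probably a typing slip in one cell of a descriptive safety table, and that raised glucose will be visible elsewhere. Much of that stands:
- SAP section 5.4.2 also provides summaries by visit, shifts against the normal range, and a further output: "Listings will be provided for patients with any laboratory results outside the reference ranges". Urine glucose has its own PCS criterion (1+ or more).
- HbA1c is measured at Screening, Baseline and Week 12, and at Weeks 24, 36, 52 and 54. With no row in Table 4, it is untouched by the fault.
- Under Protocol section 8.4, investigators review each laboratory report and record clinically relevant changes as adverse events, which are tabulated independently of the PCS flag.
- The low limit in the same row still works.
- Few patients might be flagged even under a corrected limit. Insulin and hypoglycemic agents are not allowed (Protocol Attachment 1), and a history of significant metabolic disorder is excluded (exclusion criterion 12).

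These points limit the harm; they do not make the threshold usable. A shift across the normal range does not show how far above it a value lies, which is the purpose of a PCS count. The restricted population makes values beyond 22.8 mmol/L less likely still, so the written flag becomes even less informative.

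The range of 41.8 to 46.4 mmol/L depends on an assumed UNL. The 22.8 mmol/L bound and the comparison with the other multiples do not.

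**Conclusion.** The concern holds. As written, the high fasting-glucose criterion is above 22.8 mmol/L (411 mg/dL) on the table's own figures and 41.8 to 46.4 mmol/L if UNL is 5.5 to 6.1 mmol/L. Its multiple is 2.5 times the largest other multiple in Table 4, in the only row that pairs an absolute low limit with a UNL multiple on the high side.

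That the flag will register almost no one is a judgment resting on this height and on the restricted population; the documents give no expected glucose distribution. The effect is confined to the high-glucose entries in Table 14.3.4.5 and Listing 16.2.8.1.7, with the open-label listing included by inference. Which value was intended cannot be settled from the documents. The point should be corrected, but it does not bear on the efficacy conclusions.

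**What to change.** Before unblinding, the sponsor should check the cell against the issued SAP and confirm the intended reporting threshold for high fasting glucose. The form of the row points toward an absolute SI value with a stray multiplier, but a mistyped multiple is also possible, so the choice is the sponsor's to make and document.

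Then correct the Table 4 cell and verify that the programmed flag behind Table 14.3.4.5 and Listing 16.2.8.1.7 uses the corrected limit in both phases. The differing titles of Listing 16.2.8.1.7 can be aligned at the same time.

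The cost is one table cell and a programming check.

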**NOTE:** Patients to be contacted via phone at Weeks 5, 6, 7, 9, 10, and 11 to verify safety and to make sure the patient is doing well and is compliant with study medication. **Abbreviations:** AIMS = Abnormal Involuntary Movement Scale; BARS = Barnes Akathisia Scale;

CGI-S = Clinical Global Impression-Severity Scale; CYP = cytochrome; ECG = electrocardiogram; EOS = end-of-study; HbA1c = hemoglobin A1c; HBsAg = surface antigen of hepatitis B virus; HCV = hepatitis C virus; HIV = human immunodeficiency virus; MINI = Mini International Neuropsychiatric Interview; PANSS = Positive and Negative Syndrome Scale; PSP = Personal and Social Performance; RDQ = Readiness for Discharge Questionnaire; SAS = Simpson-Angus Scale; STS = Suicidality Tracking Scale.

Footnotes:

- a Visits 7 to 13 may occur  $\pm$  2 days from scheduled visit.
- b Visits 2-5 hospitalization may be extended at the discretion of the investigator. Hospitalization on Visits 6 and 7 are at the discretion of the investigator to ensure per-protocol ECG assessment and PK sampling are done. Hospitalization includes admission to a hospital or the utilization of an inpatient facility.
- c Vital signs (blood pressure, heart rate, respiratory rate, and oral or aural body temperature) obtained after the patient is resting in supine position for ≥ 5 minutes. Vital signs during hospitalization are assessed pre-dose within 30 minutes of dosing, and at about 4 hours post dosing. All other assessments are at about 4 hours post dosing.
- d Height only at Screening Visit; Patients will be weighed clothed (lightly) and without shoes at every indicated visit.
- e Scheduled ECG recordings (in triplicate) should be obtained after the patient is resting in supine position for ≥ 10 minutes. Three triplicate ECG assessments (9 assessments) should be performed on Day -1 to serve as the Baseline value. Scheduled ECG recording during hospitalization (Visits 4 through 7 and Visit 11) should be done prior to the planned PK sample at pre-dose within 30 minutes of dosing, and at the approximate time of maximum plasma concentration of both MIN-101 (6 to 8 hours post dosing) and BFB-520 (9 to 12 hours post dosing). Scheduled ECG recordings on Visits 8 to 10 should be done prior to the planned PK sample 2-4 hours post dosing after all other assessments have been completed.

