#### Footnotes:

- a Visits 7 to 13 may occur  $\pm$  2 days from scheduled visit
- b Visits 2-5 hospitalization may be extended at the discretion of the investigator Hospitalization on Visits 6 and 7 are at the discretion of the investigator to ensure per-protocol ECG assessment and PK sampling are done Hospitalization includes admission to a hospital or the utilization of an inpatient facility
- c Vital signs (blood pressure, heart rate, respiratory rate, and oral or aural body temperature) obtained after the patient is resting in supine position for ≥ 5 minutes Vital signs during hospitalization are assessed pre-dose within 30 minutes of dosing, and at about 4 hours post dosing All other assessments are at about 4 hours post dosing
- d Height only at Screening Visit; Patients will be weighed clothed (lightly) and without shoes at every indicated visit
- Scheduled ECG recordings (in triplicate) should be obtained after the patient is resting in supine position for ≥ 10 minutes. Three triplicate ECG assessments (9 assessments) should be performed on Day -1 to serve as the Baseline value. Scheduled ECG recording during hospitalization (Visits 4 through 7 and Visit 11) should be done prior to the planned PK sample at pre-dose within 30 minutes of dosing, and at the approximate time of maximum plasma concentration of both MIN-101 (6 to 8 hours post dosing) and BFB-520 (9 to 12 hours post dosing). Scheduled ECG recordings on Visits 8 to 10 should be done prior to the planned PK sample 2-4 hours post dosing after all other assessments have been completed.
- f Safety laboratory tests include haematology, serum chemistry (including serum lipid profile, and fasting blood glucose) and prolactin Patients must fast for 8 hours before the blood sample is taken Baseline safety laboratory tests will be performed no later than Day -2 (and not earlier than Day -5) to ensure results are available prior to the first study drug administration
- E Dipstick urinalysis will be completed on site at Screening, Baseline, and Weeks 4, 8, 12 (or early termination) Urine specimen will only be sent to the central laboratory for microscopic analysis in the event the dipstick results are abnormal

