## 3.3.7. Presentations by Time Point

Visit designations used in statistical analyses will be derived by aligning actual visit dates within visit date windows as shown in Table 1. If assessments are collected multiple times within a given visit window, the result closest to the target day will be used for summary presentations. If two measurements have the same distance to the target day, the earlier value will be used. All planned, Unscheduled, and Early Termination assessments will be categorized similarly. All assessments will be presented in the listings.

Table 1 Visit Designations

Derived Visit	Scheduled Visit (Day a )	a Target Day						
Baseline	Day -1		Days [-28, 1] and prior to first dose of study drug					
Day 1	Day 1	1	Day [1]					
Day 2	Day 2	2	Day [2]					
Week 1	Week 1	8	Days [3,11]					
Week 2	Week 2	15	Days [12, 18]					
Week 3	Week 3	22	Days [19, 25]					
Week 4	Week 4	29	Days [26, 43]					

Derived Visit	Scheduled Visit (Day a )	Target Day	Window [lower bound, upper bound] b				
Week 8	Week 8	57	Days [44, 71]				
Week 12 End of double- blind treatment period c	Week 12	85	Days 72 through last day of double-blind treatment period.  Final or termination visit during the double-blind treatment phase				
Week 12.1	Week 12 + 1	87	First day of open-label treatment				
Week 12.2	Week 12 + 2	88	First day of open-label treatment + 1				
Week 13	Week 13	92	First day of open-label treatment + 2 through Day 9				
Week 14	Week 14	99	Days [96, 102]				
Week 15	Week 15	106	Days [103, 109]				
Week 16	Week 16	113	Days [110, 127]				
Week 20	Week 20	141	Days [128, 155]				
Week 24	Week 24	169	Days [156, 183]				
Week 28	Week 28	197	Days [184, 211]				
Week 32	Week 32	225	Days [212, 239]				
Week 36	Week 36	253	Days [240, 267]				
Week 40	Week 40	281	Days [268, 295]				
Week 44	Week 44	309	Days [296, 323]				
Week 48	Week 48	337	Days [323, 351]				
Week 52	Week 52	365	Days [352, 372]				
Week 54 EOS period c			Final or termination visit during the open-label treatment period; date will be earlier if early study termination occurred.				

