## 3.3.8. Definitions and Terminology

#### Baseline Value

Baseline will be defined as the last valid evaluation done before the study drug administration on Day 1. For ECG, the mean of the 3 triplicate ECG assessments (9 assessments) performed on Day -1 will serve as the Baseline value.

#### Day 1

Day 1 is the earliest day that study drug is first initiated.

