#### 5.4.4. Assessment of Vital Signs

Descriptive summaries of vital signs data including oral or aural temperature, respiratory rate, pulse, and blood pressure (systolic and diastolic) and respective changes from Baseline, will be presented by time point and treatment group. Three consecutive blood pressure and pulse readings are recorded at each assessment time point and all blood pressure and pulse analyses will be based on the average of triplicate measurements.

The number and percentage of patients with any PCS vital sign occurring post-Baseline will also be summarized by time point and treatment group (Table 5). All vital signs will be listed with PCS vital signs flagged.

Table 5 Criteria for Potentially Clinically Significant Vital Signs

Parameter	Flag	Criteria Observed Value
Contain his advances (months)	High	≥ 150
Systolic blood pressure (mmHg)	Low	≤ 90
Diastolic blood pressure (mmHg)	High	≥ 100
Diastone blood pressure (mining)	Low	≤ 50
Hand water/Data and a (larger)	High	≥ 110
Heart rate/Pulse rate (bpm)	Low	≤ 50
Tomporatura (9C)	High	≥ 38
Temperature (°C)	Low	< 35

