#### 5.4.5. ECG Assessments

ECG measurements will be provided by a central reader.

ECGs are recorded in triplicate one minute apart, and all ECG analyses will be based on the average of triplicate measurements. The mean of the 3 triplicates (9 assessments) performed on Day -1 will be used as the Baseline for all analyses of that safety parameter.

ECG variables and their change from Baseline will be summarized with descriptive statistics by time point and treatment group. ECG variables will include heart rate, PR interval, RR interval, QRS interval, QT interval, and QTc interval corrected for heart rate using Fridericia's correction, QTcF.

QTcF values will also be tabulated for their absolute values and tabulated relative to Baseline measurements in order to detect individual QTcF changes. Additionally, the number and percentage of patients who meet the PCS values defined in Table 6 will be summarized.

Table 6 Criteria for Potentially Clinically Significant ECG Parameters

			Criteria
Parameter	Flag Observed Value		Change from Baseline or Observed Value
Heart Data (hous)	High	> 110	
Heart Rate (bpm)	Low	≤ 50	
QTcF a Interval (msec)	High Male	> 450	>30-60, > 60, > 450-480,
Q'Tel' Interval (insee)	High Female	> 470	> 480-500, > 500
QRS Interval (msec)	High	> 120	
PR Interval (msec)	High	> 220	

<sup>a QTc interval is derived as: QTcF=QT Interval (msec) / (RR (msec)/1000)(1/3)

To understand the effect of treatment arm on the change in QTcF, an ANCOVA will be performed by assessment times (visit and timepoint within visit) using the change from Baseline (as dependent variable) with treatment arm (MIN-101 32 mg, MIN-101 64 mg, and placebo) as a factor, and Baseline value as covariate. Estimates for the difference at each assessment time for each dose group versus placebo, standard error of the mean, and the upper bound of the 2-sided 90% confidence intervals will be presented.

Important abnormalities in ECG waveform that are changes from Baseline readings will also be reported in a listing, as well as PCS ECG parameters.

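### The SAP's counts of potentially clinically significant (PCS) values do not exclude patients who already met the limit at Baseline, and leave the Day 1 pre-dose ECG unassigned

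*SAP*

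**What the plan says.** For laboratory tests, SAP 5.4.2 states that the number and percentage of patients "experiencing PCS laboratory abnormalities post-baseline will be summarized by treatment group", using the limits in Table 4. For vital signs, 5.4.4 states: "The number and percentage of patients with any PCS vital sign occurring post-Baseline will also be summarized by time point and treatment group", using Table 5. For ECG, 5.4.5 states that "the number and percentage of patients who meet the PCS values defined in Table 6 will be summarized". The corresponding table title in SAP 9.1 restricts the ECG count to post-Baseline findings.

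Two kinds of criterion refer to the Baseline value: low hematocrit in Table 4, which also needs a fall from baseline, and the QTcF increase categories in Table 6. The rest of Table 4, all of Table 5 and the heart rate, PR and QRS rows of Table 6 are limits on the observed value.

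SAP 3.3.8 gives the general rule: "Baseline will be defined as the last valid evaluation done before the study drug administration on Day 1". It then makes an exception: "For ECG, the mean of the 3 triplicate ECG assessments (9 assessments) performed on Day -1 will serve as the Baseline value". Table 1 in 3.3.7 sets the Baseline visit window as "Days [-28, 1] and prior to first dose of study drug" and also has a separate Day 1 row covering Day 1.

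**The concern.** A patient who enters with, say, systolic pressure at or above 150 mmHg, pulse at or below 50, cholesterol above 7.75 mmol/L or lymphocytes at or above 4.0, and who stays there, is counted as a PCS case under the assigned treatment although nothing changed on treatment. This raises the percentage in every arm, placebo included, pulls the drug-placebo ratio toward 1 and adds noise when such patients fall unevenly across arms.

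The SAP applies a stricter principle to adverse events: 3.3.8 ties a treatment-emergent event to the start of treatment, and 5.4.1 keeps earlier events out of the tables. The PCS tables have no equivalent.

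ECG raises a second question. With Baseline fixed on Day -1, a recording made on Day 1 before the first dose comes after Baseline but before drug. QT prolongation is the risk that the protocol stresses (1.5), so it should be clear whether a pre-drug QTcF change can enter a threshold table.

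**Working it through.** **1. Can patients enter already beyond a limit?** Entry criteria in Protocol 4.2, set against the PCS limits:

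- QTcF: entry excludes > 430 msec (male) and > 450 msec (female); PCS is > 450 and > 470. Protected.
- Potassium: entry excludes < 3.4 mmol/L; PCS low is < 3.3. Protected.
- Calcium: entry excludes < 2.07 mmol/L; PCS low is < 1.97. Protected.
- Blood pressure, pulse, PR, QRS, cholesterol, lymphocytes, hemoglobin: no numeric entry limit. Attachment 1 permits chronic antihypertensives and hypolipidemics.

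**2. Do the shift tables fill the gap?** The laboratory shift in 5.4.2 uses the normal range, not the PCS limits, and runs from Baseline to Week 12 or early termination, so a value that appears only at Week 4 or 8 is missed. Vital-sign and ECG shift tables are listed in 9.1, but neither 5.4.4 nor 5.4.5 defines their categories.

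**3. Size.** The documents give no PCS rates, so these inputs are assumptions: Baseline prevalence b, share persisting s, new-onset rate e of 2% on placebo and 6% on drug (true ratio 3.0, difference 4.0 points). The planned arm size is 167 (SAP 3.1).

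Displayed rate = b·s + (1 − b)·e. For b = 5%, s = 1: placebo 0.05 + 0.95 × 0.02 = 6.9%; drug 0.05 + 0.95 × 0.06 = 10.7%.

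| b | s | Placebo | Drug | Ratio | Difference (points) | Pre-existing cases per arm (167·b·s) |
|---|---|---|---|---|---|---|
| 2% | 1 | 4.0% | 7.9% | 2.0 | 3.9 | 3.3 |
| 5% | 1 | 6.9% | 10.7% | 1.55 | 3.8 | 8.4 |
| 10% | 1 | 11.8% | 15.4% | 1.31 | 3.6 | 16.7 |
| 2% | 0.5 | 3.0% | 6.9% | 2.3 | 3.9 | 1.7 |
| 5% | 0.5 | 4.4% | 8.2% | 1.9 | 3.8 | 4.2 |
| 10% | 0.5 | 6.8% | 10.4% | 1.5 | 3.6 | 8.4 |

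The difference equals (1 − b) × 4.0 whatever s is, which is why it barely moves.

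Chance imbalance: the SD of the between-arm difference in Baseline prevalence is √(2b(1 − b)/167), which is 1.5, 2.4 or 3.3 points for b = 2%, 5% or 10%. With full persistence nearly all of it passes into the displayed difference.

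**4. Is post-Baseline the same as post-dose?** For labs and vital signs, yes: under the general rule in 3.3.8, any value taken before the first dose is either the Baseline value or earlier. For ECG it need not be. The protocol's double-blind schedule says: "Scheduled ECG recording during hospitalization (Visits 4 through 7 and Visit 11) should be done prior to the planned PK sample at pre-dose". Visit 4 is Day 1. Of the scheduled double-blind ECG assessments after Day -1 (three each at Visits 4 to 7 and 11, one each at Visits 8 to 10: 5 × 3 + 3 × 1 = 18), one is pre-drug. Section 3.3.8 puts it after Baseline; the Table 1 window puts it inside Baseline. Neither 5.4.5 nor the table titles settle which applies.

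**The case against.** Several points on the other side stand.

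- Protocol exclusion 15 removes clinically significant hematology, chemistry, ECG or examination abnormalities that the investigator judges can interfere with participation, exclusion 12 removes major or unstable cardiovascular and other disease, and Protocol 8.1.2.2 requires Baseline labs and centrally read ECGs to be reviewed before randomization. These should lower the prevalence of Baseline PCS values, but they rest on judgment and are not the PCS limits.
- The tables are descriptive, with no hypothesis test on PCS rates, and change-from-Baseline summaries and listings let a reader trace individual pre-existing cases. Listings do not, however, give a between-arm count of new cases.
- Counting every post-Baseline value is inclusive and keeps patients who worsen from an abnormal start. A separate row for Baseline-positive patients keeps them too.

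Some stronger readings are tempting but unsupported. A reader might infer that pre-drug values enter all the PCS tables; for labs and vital signs the definition of Baseline rules this out. A reader might take the Day 1 pre-dose ECG as plainly post-Baseline; Table 1 points the other way, so it is an ambiguity. A reader might suppose that the QTcF ANCOVA is contaminated; 5.4.5 fits it by visit and time point, so a Day 1 pre-dose estimate would stand alone. And a reader might suppose that the absolute drug-placebo difference is materially diluted; the arithmetic shows that it is not.

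**Conclusion.** The concern holds for the laboratory limits (hematocrit excepted), the vital-sign limits and the heart rate, PR and QRS rows of Table 6: nothing removes patients who met the limit at Baseline. The consequences are higher percentages in every arm, a diluted ratio (3.0 falling to between 2.3 and 1.3 across the assumed range) and added noise from chance Baseline imbalance; the difference stays within 0.4 points of the true 4.0. These sizes rest wholly on assumed prevalence, persistence and new-onset rates. Observed-value QTcF, low potassium and low calcium are largely protected by entry limits. The status of the Day 1 pre-dose ECG in the PCS and QTcF threshold tables is a separate, unresolved ambiguity. This is a worthwhile, inexpensive improvement to descriptive safety tables; it does not touch the efficacy conclusions.

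**What to change.** In SAP 5.4.2, 5.4.4 and 5.4.5, define treatment-emergent PCS as the criterion being met at an assessment after the first dose by a patient who did not meet it at Baseline. Use as denominator the patients not meeting it at Baseline who have at least one post-dose value. Show patients who met it at Baseline in a separate row, so that no one is lost from view. State that the Day 1 pre-dose ECG is pre-treatment and is excluded from the PCS and QTcF threshold counts. The by-timepoint QTcF ANCOVA needs no change.

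The cost is SAP wording and table programming on data already collected. The downside is that denominators will differ slightly from one parameter to another.
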